## 9.8 Statistical Analysis Plan

### 9.8.1 Primary analysis

RFS is defined as the time from randomization to the time of disease recurrence or death from any cause. OS is defined as the time from randomization to the time of death due to any cause. Both RFS and OS will serve as co-primary endpoints in this study. When 50% information time (208 deaths among patients treated with low dose Ipi or HDI) is reached for OS, the first interim analysis will begin. To preserve overall type I error rates for both RFS and OS endpoints, the hierarchical testing will be implemented separately for RFS and OS endpoints. Interim analyses of high dose Ipi vs. HDI for RFS will begin once low dose Ipi vs. HDI is significant for RFS (and only if it is) and interim analyses of high-dose Ipi vs. HDI for OS will begin once low dose Ipi vs. HDI is significant for OS (and only if it is).

Similarly during the final analysis, if low dose Ipi vs. HDI is significant for RFS at the 0.3% level, then we will compare RFS between high dose Ipi vs. HDI at the 0.3% level. If low dose Ipi vs. HDI is significant for OS at the 2.2% level, then we will compare high dose Ipi vs. HDI at the 2.2% level. These two decisions will be made separately and if only RFS is significant for low dose Ipi vs. HDI, then only RFS will be compared for high dose Ipi vs. HDI. Similarly if only OS is significant to low dose Ipi vs. HDI, then only OS would be compared for the high dose arm.

The primary comparison will be an ITT analysis including all cases as randomized using the stratified (by AJCC stages: IIIB, IIIC, M1a, M1b)

log-rank test. Kaplan-Meier plot will be generated and two-sided p-values will be reported.

During the interim analysis, data available as of the data cut-off date for a specified interim analysis will be included. Specific guidelines outlined in section 9.6 will be used. Briefly, for the efficacy analysis, the type I error rate will be allocated per truncated O'Brien-Fleming boundary (equivalent to O'Brien-Fleming boundary in our case since the first analysis will not begin until 50% information time). For the futility analysis, the conditional power will be calculated. Hazard ratio will be estimated and repeated confidence intervals will be generated for OS and RFS.

At the final analysis, all cases will be included. If the proportional hazard assumption is appropriate, multivariate Cox proportional hazard models for RFS and OS will be developed at the final analysis. Prognostic factors such as age, gender, stage, ulceration, etc will be included. For the stratified log-rank test and Cox proportional hazards regression model, sensitivity analysis will be conducted at the final analysis based on analyzable (eligible and treated) patients only.

At the final analysis, if the low-dose Ipi vs. HDI is significant and high-dose Ipi vs. HDI is significant for OS then OS will be compared for the low-dose Ipi vs, high-dose Ipi arms. Similarly, if the low-dose Ipi vs. HDI is significant and high-dose Ipi vs. HDI is significant for RFS then RFS will be compared for the the low-dose Ipi vs, high-dose Ipi arms. It is likely this comparison will be underpowered.

#### 9.8.2 Toxicity data analysis

Adverse events (AE) data will be summarized based on the data collected in ECOG CRFs as well as the data reported via CTEP-AERS. Individual toxicity type AE and categorized AE data (by autoimmune disorders, endocrine, GI, liver, nervous system, pancreas, psychiatric disorders, skin, thromboembolic disorders) will be summarized by grade and treatment arm. The percentages of patients experiencing the worst degree toxicities (highest grade event per AE type per patient) will be evaluated and the distribution of the worst degree toxicities will be compared among the treatment arms. The proportion of patients with worst degree toxicities with 3 or higher will be summarized and compared among the treatment arms. Chi-square test will be used for AE comparisons. For the AE data, any patient who received treatment will be included.

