	Unexpected and Expected	Unexpected	Expected	Unexpected with Hospitalization	Unexpected without Hospitalization	Expected with Hospitalization	Expected without Hospitalization	Unexpected	Expected
Unrelated Unlikely	Not Required	Not Required	Not Required	10 Calendar Days	Not Required	10 Calendar Days	Not Required	10 Calendar Days	10 Calendar Days
Possible Probable Definite	Not Required	10 Calendar Days	Not Required	10 Calendar Days	10 Calendar Days	10 Calendar Days	Not Required	24-Hour; 5 Calendar Days	10 Calendar Days

 Adverse events with attribution of possible, probable, or definite that occur greater than 30 days after the last dose of treatment with an agent under a CTEP IND require reporting as follows:  
 CTEP-AERS 24-hour notification followed by complete report within 5 calendar days for:  
 • Grade 4 and Grade 5 unexpected events  
 CTEP-AERS 10 calendar day report:  
 • Grade 3 unexpected events with hospitalization or prolongation of hospitalization  
 • Grade 5 expected events

 Although a CTEP-AERS 24-hour notification is not required for death clearly related to progressive disease, a full report is required as outlined in the table.

Please see additional information below under section entitled "Additional instructions, requirements, and exceptions for protocol E1609"

March 2005

**NOTE:** All deaths on study require both routine and expedited reporting regardless of causality. Attribution to treatment or other cause should be provided.

• **Expedited AE reporting timelines:**

- **24 Hours; 5 calendar days** – The investigator must initially report the AE via CTEP-AERS within 24 hours of learning of the event followed by a complete CTEP-AERS report within 5 calendar days of the initial 24-hour report.
- **10 calendar days** – A complete CTEP-AERS report on the AE must be submitted within 10 calendar days of the investigator learning of the event.

- Any medical event equivalent to CTCAE grade 3, 4, or 5 that precipitates **hospitalization\* (or prolongation of existing hospitalization)** must be reported regardless of attribution and designation as expected or unexpected with the exception of any events identified as protocol-specific expedited adverse event reporting exclusions.
- Any event that results in **persistent or significant disability/incapacity, congenital anomaly, or birth defect** must be reported via CTEP-AERS if the event occurs following treatment with an agent under a CTEP IND

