##### **Protocol specific expedited reporting requirements:**

- **Bowel Perforation:** Any grade 3 or higher bowel perforation must be reported via CTEP-AERS within 10 calendar days of learning of the event regardless of the attribution and designation as expected or unexpected.
- **Immune Related Adverse Events:** Any grade 2 or higher immune related adverse event (see section [5.5.1.3](#) for definition), *excluding skin reactions*, that occurs within 70 days of the last day of protocol treatment must be reported via CTEP-AERS within 10 calendar days of learning of the event regardless of the attribution and designation as expected or unexpected. Please submit any supporting data as well (ie: autoimmune serology tests or biopsy reports). In addition, any grade 2 or higher IRAE, excluding grade 2 or 3 skin reactions, that occurs greater than 70 days after the last dose of protocol treatment with an attribution of possible, probable, or definite must also be reported via CTEP-AERS within 10 calendar days of learning of the event. Any questions regarding if an event qualifies as an IRAE can be directed to the study chair.

Rev. 2/12, 4/14

5.3.7

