7.1.4.3 Follow-up imaging studies will consist of CT (or MRI if CT cannot be done) neck/chest/abdomen/pelvis at follow up assessment time points for all patients (A PET-CT is not required, but is acceptable if done). MRI/CT brain or other imaging studies may be done as clinically indicated but are not required in the absence of clinical indications.

- 
- 7.1.5 Pathologic/cytologic confirmation for melanoma recurrence:
- 7.1.5.1 Required for recurrence in (a) solitary or in doubtful lesions, (b) cutaneous, (c) subcutaneous, (d) lymph node lesions.
  - 7.1.5.2 Should be attempted in all cases (if possible) except for brain metastases.
  - 7.1.5.3 Date of relapse is the date of first documented recurrence (by imaging or physical examination).
- 7.1.6 Radiologic follow up imaging of recurrence is required at least 4 weeks following first documentation of recurrence and before initiation of subsequent salvage therapy (given the known mechanism of action and reported progression/response patterns of ipilimumab).
- NOTE:** A 4-week "wash out" period is expected to be required in most cases on subsequent salvage clinical trials, but it will be important to capture any subsequent disease regression on E1609, which would be an indication to hold salvage therapy and either observe or resume E1609 therapy. Physician investigators are encouraged to resume E1609 therapy in patients who experience disease regression at follow up imaging following first documented melanoma recurrence.
- 7.1.7 During treatment, patients should be closely monitored for the onset of neuropsychiatric symptoms. Specific questions should be incorporated into the routine evaluation conducted at each patient visit so as to allow for early detection of neuropsychiatric symptoms.

Rev. 2/13

Rev. 2/12, 9/14	7.2 Arms A, C, D, and F: Patients Treated with Ipilimumab at 10 mg/kg (Arm A and D) or 3 mg/kg (Arm C and F)										
	Test/ Assessment	Within 4 weeks (28 days) of starting study drugs, unless stated otherwise	Induction Phase a				Week 12 ± 2 weeks	Maintenance Phase a (Until 12 weeks after the last ipilimumab dose or until relapse)		End of Study Assessment n	Follow Up l
			Day 1 ± 3 days (Week 1)	Day 22 ± 3 days (Week 4)	Day 43 ± 3 days (Week 7)	Day 64 ± 3 days (Week 10)		Week 24, 36, 48, 60 ± 2 Weeks	Every 6 Weeks ±1 Week		
Rev. 2/12	Informed Consent	X									
	History/Physical/ECOG PS	X	X	X	X	X	X	X	X	X	X

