- At screening, testing should be performed for HIV antibody, hepatitis C antibody, and HBsAg (hepatitis B antigen) utilizing local standard informed consent procedures prior to this laboratory collection. These tests could be repeated later during the course of the study if clinically indicated.
- Rev. 2/13
- h. Ophthalmologic examination will be done at baseline only if clinically indicated. On this study, the last dose of ipilimumab will be at approximately week 60. Ophthalmological examination is strongly recommended at 6 and 18 months ( $\pm$  4 weeks) after start of treatment especially in patients who experienced diarrhea or colitis, to be performed by an ophthalmologist. If melanoma recurrence occurs before these time points, the Ophthalmological examination should still be done if clinically indicated. It should also be performed at other timepoints if clinically indicated.

- i. Hormonal studies: To be done at the indicated visits and when clinically indicated. These include TSH, free T4, morning ACTH, morning cortisol. For Men: testosterone. For WOCBP: prolactin, LH, FSH, and estradiol that will be done only if a WOCBP is experiencing amenorrhea while on protocol treatment.
- Rev. 8/12 j. Until 70 days after the last study drug administration. All adverse events must be collected whether they occur on treatment or non-treatment weeks and must be submitted utilizing the corresponding E1609 Adverse Event Forms, covering all time periods specified on the forms.
- Rev. 8/12 k. **Baseline imaging studies:** should be done within 4 weeks prior to randomization. These must include a total body PET-CT scan (with or without brain) and brain MRI or CT (if MRI is contraindicated). If PET-CT cannot be done, CT of neck, chest, abdomen and pelvis should be done. If for some reason a CT cannot be done, an MRI may be done instead. Any other imaging studies if performed (e.g., bone scan) must show no evidence of disease. **During treatment and on follow-up:** CT (or MRI if CT cannot be done) neck/chest/abdomen/pelvis will be done every 3 months (-/+ 2 weeks) if patient is < 2 years from study entry, then every 6 months (+/- 4 weeks) if patient is 2-5 years from study entry, and every 12 months (+/- 4 weeks) if patient is > 5 years from study entry for up to 20 years. A PET-CT is not required, but is acceptable if done. Brain MRI/CT or other imaging studies may be done as clinically indicated but are not required in the absence of clinical indications.

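### Section 9.8.2 tests arm differences on adverse events pooled from two sources whose follow-up differs after day 70, and sets no common window

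*Combined protocol and SAP*

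**What the plan says.** **Analysis.** Section 9.8.2 names two sources: "Adverse events (AE) data will be summarized based on the data collected in ECOG CRFs as well as the data reported via CTEP-AERS". On that pool it plans that "The proportion of patients with worst degree toxicities with 3 or higher will be summarized and compared among the treatment arms", and adds: "Chi-square test will be used for AE comparisons". It gives no time window, no rule for combining the sources and no significance level. Section 9.7.1 speaks of treatment-emergent events without defining the term.

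**Forms.** Footnote j of the ipilimumab calendar (7.2) reads: "Until 70 days after the last study drug administration. All adverse events must be collected whether they occur on treatment or non-treatment weeks". Footnotes h and j of the HDI calendar (7.3) set the same 70-day stop.

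**CTEP-AERS.** Three rules govern late reports:
- The closing note of 5.3.4 keeps events beyond 30 days reportable if they are attributed to treatment and meet 5.3.6.
- Footnote 1 to the 5.3.6 table covers attributed events "greater than 30 days after the last dose of treatment with an agent under a CTEP IND". It lists Grade 4-5 unexpected events, Grade 3 unexpected events with hospitalization, and Grade 5 expected events.
- The protocol-specific rules in 5.3.6 add any immune-related event of Grade 2 or higher (Grade 2-3 skin excepted) "that occurs greater than 70 days after the last dose of protocol treatment with an attribution of possible, probable, or definite".

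None of the three states a stop. The only outer limit is a note closing 5.3.7, which ends CTEP-AERS follow-up data once survival and remission data are no longer needed. Survival follow-up is 20 years (5.8).

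**The concern.** Up to day 70 a patient's worst grade is the worst of all events. After day 70 it can rise only through events that an investigator attributes to treatment and that also pass a grade, expectedness, hospitalization or immune-related criterion. The pooled data set therefore joins complete follow-up to selective follow-up, and the test treats the two as one.

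If the filter passed late events equally in all arms, the pooled rates would be hard to interpret but the comparison would stay roughly fair. The text gives three reasons why it may not:
- **Coverage of HDI.** The note opening 5.3.6 puts all arms under the investigational reporting rules. Footnote 1 ties late reporting to a drug under a CTEP IND, which here is ipilimumab alone.
- **Expectedness.** Step 4 of 5.3.2 uses SPEER for ipilimumab and the package insert or protocol for HDI. SPEER in 5.4 holds seven terms. Section 8.2.11 alone lists interferon effects across about a dozen organ systems. A late event not labeled immune-related can thus count as unexpected on one drug and expected on the other.
- **Attribution.** No blinding is described, and the regimens differ in route and schedule, so causality is judged with the arm known.

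Safety and tolerability is the first secondary endpoint (2.2.1). Part of a tested arm difference could come from the reporting rule. The exposure is greatest in low-rate organ categories, where a few late events move the proportion.

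**Working it through.** Section 9.8.2 states no power, alpha or expected difference, so there is no figure to reproduce. The documents also give no rate of events first seen after day 70. What follows is an illustration on assumed rates.

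**Inputs**
- n = 500 per arm (9.3, approximate).
- p, the true proportion with the event inside the 70-day window, equal in both arms. Values of 3% and 5% represent organ categories: at 10 mg/kg, section 1.5.4.6.1 gives Grade 3/4 rates of 2.5% endocrine, 2.8% skin and 6.8% liver. Values of 25% and 40% represent overall Grade 3 or higher rates. All four are assumptions.
- a, the share of ipilimumab patients who have no event in the window but gain one late: 1%, 2% or 3% (assumed).
- h, HDI late capture relative to ipilimumab: 0, 0.5 or 1 (assumed).
- Uncorrected chi-square at 3.841, two-sided 5% (assumed).

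**Formulas**
- Ipilimumab proportion: p + a(1 - p).
- HDI proportion: p + h·a(1 - p).
- Standard error of the difference at the base rate: sqrt(2p(1 - p)/n).
- Rejection probability: exact sum over two binomials of size 500.

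**Scale of the shift for a = 1%, h = 0**
- p = 3%: shift 0.01 × 0.97 = 0.97 points; SE = sqrt(2 × 0.03 × 0.97/500) = 1.08 points; ratio 0.90.
- p = 5%: shift 0.95 points; SE 1.38; ratio 0.69.
- p = 40%: shift 0.60 points; SE 3.10; ratio 0.19.

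**Probability of a significant difference although the 70-day rates are equal**

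| p | HDI late capture | a = 1% | a = 2% | a = 3% |
|---|---|---|---|---|
| 3% | none | 13% | 35% | 61% |
| 3% | half | 7% | 11% | 18% |
| 3% | equal | 5% | 5% | 5% |
| 5% | none | 10% | 24% | 45% |
| 5% | half | 6% | 9% | 14% |
| 5% | equal | 5% | 5% | 5% |
| 25% | none | 6% | 8% | 13% |
| 40% | none | 5% | 7% | 9% |

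The rows with no HDI capture are the upper end. They require that footnote 1 prevails over the all-arms note and that no immune-related late event is attributed to interferon.

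The late immune-related rule admits Grade 2 events as well. These move the worst-grade distribution but not the Grade 3 or higher proportion, so the table applies only to the latter.

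**The case against.** A reader might infer that the comparison is biased against ipilimumab as a matter of fact. The documents do not establish that:
- The form stop is 70 days in every arm.
- The 5.3.6 note extends the expedited rules to HDI, and the late immune-related rule refers to protocol treatment generally.
- The immune-related definition in 5.5.1.3 sits in the ipilimumab section but names no drug. The HDI modification table (5.5.2.8) has its own autoimmune entries, and footnote m of 7.3 orders autoantibody tests on HDI to week 96. A late attributed thyroid event on interferon is therefore reportable.
- Some influences run the other way. Section 1.7.2 expects HDI patients to receive ipilimumab off protocol at recurrence. Toxicity from that drug within 70 days of the last interferon dose would count against HDI.
- Late ipilimumab toxicity is partly real. A footnote in 5.4 says a minority of immune reactions appear weeks to months after stopping.

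Two other readings also fail. The HDI calendar header ends maintenance assessments earlier than the ipilimumab header, but footnotes h and j carry adverse-event collection to 70 days there too. And CTEP-AERS is not wholly without an outer limit, given the note in 5.3.7, although that limit is distant.

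It can also be said that 2.2.1 asks to evaluate ipilimumab's safety, not to compare it with HDI. Even so, 9.8.2 plans between-arm tests. The Forms Packet, which sets the form periods in detail, is not part of the documents.

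These points limit the direction and the size. They leave untouched the two different stops, the pooling and the missing window.

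**Conclusion.** The defect stands: 9.8.2 mixes complete follow-up to day 70 with filtered follow-up afterwards and tests the result between arms. The comparison can be distorted. A shift against ipilimumab is the more plausible direction, because of the CTEP IND footnote, the two expectedness references and attribution with the arm known. Neither direction nor size is established.

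The percentages are illustrations that rest on assumed late-event rates and assumed HDI capture. They matter for categories of about 3-5%. They shrink to 6-18% at half capture, vanish at equal capture, and are modest for overall Grade 3 or higher rates (5-13% even with no HDI capture). The primary RFS and OS analyses are not affected.

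**What to change.** In 9.8.2:
- Define the compared data set as all adverse events from first dose to 70 days after the last dose, in every arm.
- Use CTEP-AERS only to reconcile events inside that window, and state how an event found in both sources is counted once.
- Tabulate events after day 70 separately by arm, with no between-arm test.
- Reconcile the all-arms note of 5.3.6 and the note in 5.3.4 with footnote 1 of the 5.3.6 table on whether late reporting covers HDI, and state in the late-event table which rule applied.

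The cost is SAP wording and one extra table. The downside is that late immune-related events leave the tested rates and appear only in that table. The common rule also does not equalize calendar time: planned treatment of about 60 weeks on ipilimumab and 52 on HDI (5.7.1) gives windows of about 60 + 10 = 70 and 52 + 10 = 62 weeks. The report should say so.

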- b. For first infusion only, vital signs to be collected prior to dosing, every 15 minutes during dosing and 30 - 60 minutes after dosing until vital signs normalize or return to baseline. For subsequent infusions, vital signs should be collected prior to dosing, every 30 minutes during dosing, and 1 hour post dosing.
- c. Hematology labs to include hemoglobin, hematocrit, red blood cell count, white blood cell count, platelets (direct platelet count), as well as total and differential CBC counts. The CBC differential includes enumeration of neutrophils, lymphocytes, eosinophils, monocytes, basophils and any abnormal blood cells. These labs must be done and reviewed before ipilimumab infusion. These labs are required to be done throughout follow-up regardless if the patient goes off treatment early for anything other than recurrence. Once recurrence occurs, these labs are no longer required to be completed unless clinically indicated for safety purposes as per the standard of care for these patients.
- Rev. 8/12
- d. Chemistry laboratory analysis includes albumin, amylase, lipase, urea or BUN, creatinine, ALT, AST, LDH, serum alkaline phosphatase, direct and total bilirubin, glucose, total protein, sodium, potassium, chloride, HCO3 (CO2; venous blood), calcium, phosphorous. In follow up (after completion of ipilimumab treatment), amylase and lipase will be done only if clinically indicated. These labs must be done and reviewed before ipilimumab infusion. These labs are required to be done throughout follow-up regardless if the patient goes off treatment early for anything other than recurrence. Once recurrence occurs, these labs are no longer required to be completed unless clinically indicated for safety purposes as per the standard of care for these patients.
- Rev. 2/13
- e. Urinalysis will be done as clinically indicated. Urinalysis tests to include gross examination including specific gravity, protein, glucose and blood. A microscopic evaluation will also be performed, as clinically indicated, to include WBC/HPF, RBC/HPF and any additional findings.
- f. WOCBP must have a negative serum or urine pregnancy test (minimum sensitivity 25 IU/L or equivalent units of HCG) at screening. Serum or urine pregnancy test must be done within 72 hours prior to each dose of ipilimumab.
- Rev. 8/12

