  - b. Hematology labs to include hemoglobin, hematocrit, red blood cell count, white blood cell count, platelets (direct platelet count), as well as total and differential CBC counts. The CBC differential includes enumeration of neutrophils, lymphocytes, eosinophils, monocytes, basophils and any abnormal blood cells. These labs are required to be done throughout follow-up regardless if the patient goes off treatment early for anything other than recurrence. Once recurrence occurs, these labs are no longer required to be completed unless clinically indicated for safety purposes as per the standard of care for these patients.
  - c. Chemistry laboratory analysis includes albumin, creatine kinase (CPK), urea or BUN, creatinine, ALT, AST, LDH, serum alkaline phosphatase, direct and total bilirubin, glucose, total protein, sodium, potassium, chloride, HCO3 (CO2; venous blood), calcium, phosphorous. These labs are required to be done throughout follow-up regardless if the patient goes off treatment early for anything other than recurrence. Once recurrence occurs, these labs are no longer required to be completed unless clinically indicated for safety purposes as per the standard of care for these patients.
  - d. Urinalysis will be done as clinically indicated. Urinalysis tests to include gross examination including specific gravity, protein, glucose and blood. A microscopic evaluation will also be performed, as clinically indicated, to include WBC/HPF, RBC/HPF and any additional findings.
  - e. WOCBP must have a negative serum or urine pregnancy test (minimum sensitivity 25 IU/L or equivalent units of HCG) at screening. Serum or urine pregnancy test should also be done within 72 hours of the first dose of HDI, then during HDI therapy every 4 weeks x3 (-/+ 1 week), then every 6 weeks (-/+ 1 week) and ending with the discontinuation of HDI. At HDI discontinuation, a negative pregnancy test within the preceding 6 weeks is sufficient. A pregnancy test should also be done at anytime if there are clinical concerns for possible pregnancy.
  - f. At screening, testing should be performed for HIV antibody, hepatitis C antibody, and HBsAg (hepatitis B antigen) utilizing local standard informed consent procedures prior to this laboratory collection. These tests could be repeated later during the course of the study if clinically indicated.

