  - g. Hormonal studies: To be done at the indicated visits and when clinically indicated. These include TSH, free T4.
  - h. Until 70 days after the last study drug administration. All adverse events must be collected whether they occur on treatment or non-treatment weeks and must be submitted utilizing the corresponding E1609 Adverse Event forms, covering all time points specified on the forms.
  - i. **Baseline imaging studies:** should be done within 4 weeks prior to randomization. These must include a total body PET-CT scan (with or without brain) and brain MRI or CT (if MRI is contraindicated). If PET-CT cannot be done, CT of neck, chest, abdomen and pelvis should be done. If for some reason a CT cannot be done, an MRI may be done instead. Any other imaging studies if performed (e.g., bone scan) must show no evidence of disease. **During treatment and on follow-up:** CT (or MRI if CT cannot be done) neck/chest/abdomen/pelvis will be done every 3 months (-/+ 2 weeks) if patient is < 2 years from study entry, then every 6 months (+/- 4 weeks) if patient is 2-5 years from study entry, and every 12 months (+/- 4 weeks) if patient is > 5 years from study entry for up to 20 years. A PET-CT is not required, but is acceptable if done. Brain MRI/CT or other imaging studies may be done as clinically indicated but are not required in the absence of clinical indications.

- Rev. 2/12,  
2/13
- j. Follow up period will start 12 weeks after the last interferon dose for patients who have no disease progression. These patients should be seen at 6 weeks (-/+ 1 week) after the last dose then 12 weeks (-/+ 1 week) after the last dose and later evaluated per the standard ECOG-ACRIN follow-up schedule. Every 3 months (+/- 2 weeks) if patient is < 2 years from study entry, every 6 months (+/- 4 weeks) if patient is 2-5 years from study entry, and every 12 months (+/- 4 weeks) if patient is > 5 years from study entry for up to 20 years. However, patients with ongoing toxicities should be seen more often as clinically indicated. Patients who develop recurrent melanoma will be followed for survival and for information on salvage patterns. The schedule of clinical follow up for these patients will be at the discretion of the treating physicians and according to established Standard of Care. Adverse Events Assessment on the study will continue for all patients until 70 days after the last study drug administration.
- Rev. 9/14

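### Section 9.8.2 tests AE grades across all arms, but several laboratory tests are scheduled only on ipilimumab or only on HDI, so ipilimumab-versus-HDI differences in laboratory-detected events can arise from testing alone

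*Combined protocol and SAP*

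**What the plan says.** Section 9.8.2 (Toxicity data analysis) summarizes individual and categorized adverse events by grade and arm, using nine categories that include endocrine and pancreas. It then plans comparisons: "the distribution of the worst degree toxicities will be compared among the treatment arms", and "The proportion of patients with worst degree toxicities with 3 or higher will be summarized and compared among the treatment arms". The method is a single sentence: "Chi-square test will be used for AE comparisons". The HDI arm is not excluded, and no significance level is given. Section 9.7.1 states that biochemical toxicities based on laboratory measurements are summarized by treatment group and worst CTCAE grade.

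The scheduled laboratory work is set out in the footnotes to the two study calendars.

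- Chemistry on ipilimumab (7.2, footnote d): "Chemistry laboratory analysis includes albumin, amylase, lipase, urea or BUN, creatinine, ALT, AST, LDH", followed by further analytes that do not include CPK.
- Chemistry on HDI (7.3, footnote c): "Chemistry laboratory analysis includes albumin, creatine kinase (CPK), urea or BUN, creatinine, ALT, AST, LDH", followed by the same further analytes; amylase and lipase are absent.
- Hormonal studies on ipilimumab (7.2, footnote i): "These include TSH, free T4, morning ACTH, morning cortisol. For Men: testosterone".
- Hormonal studies on HDI (7.3, footnote g): "These include TSH, free T4", and nothing more.

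**The concern.** A chi-square test on event counts treats a patient who was never tested as a patient without the event. An asymptomatic lipase, cortisol or testosterone abnormality can be found at a scheduled draw on ipilimumab and go unseen on HDI. For CPK the reverse holds. Two arms with the same true rate can then show different recorded rates, and the test would attribute the gap to treatment.

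At stake is the reading of ipilimumab's safety against HDI for these event types. Safety and tolerability is the first secondary objective listed (2.2.1), and section 12.1 says the study will support a US marketing application. The direction is predictable: pancreatic, adrenal and testosterone findings are raised on ipilimumab relative to HDI, and CPK findings on HDI relative to ipilimumab.

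**Working it through.** **Plan figure.** There is none to reproduce. The documents give no expected rate, power or significance level for the AE comparisons.

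**Step 1: the schedules side by side.**

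| Analyte | Ipilimumab (7.2) | HDI (7.3) |
|---|---|---|
| Amylase, lipase | scheduled (only if clinically indicated after treatment ends) | not scheduled |
| Morning ACTH, morning cortisol | scheduled | not scheduled |
| Testosterone (men) | scheduled | not scheduled |
| CPK | not scheduled | scheduled |
| TSH, free T4 | scheduled | scheduled |
| Other listed chemistry and hematology | scheduled | scheduled |

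**Step 2: do such results become graded events?** The protocol treats them as such. The ipilimumab dose-delay criteria (5.5.1.1.1 and 5.5.1.2.1) name amylase, lipase and CPK among immune-related laboratory abnormalities of grade 2 or above. The exceptions to permanent discontinuation (5.5.1.1.4 and 5.5.1.2.4) refer to grade 2 low testosterone and grade 2 adrenal insufficiency. The HDI table in 5.5.2.8 sets CPK thresholds.

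**Step 3: does the plan deal with the difference?** Sections 9.7.1, 9.8.2 and 9.8.3 do not restrict tests to analytes scheduled in every arm, separate laboratory-only from clinical events, or add a caveat.

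**Step 4: how large could the effect be?** This is an illustration. From the documents: about n = 500 per arm (9.3). Assumed: two-sided alpha of 0.05; the same true rate t of a laboratory-only event in both arms; every event found where the test is scheduled; and a fraction d found where it is not. Then p1 = t, p2 = d × t, p̄ = (p1 + p2)/2, and

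- se0 = √[2 p̄(1 − p̄)/n]
- se1 = √{[p1(1 − p1) + p2(1 − p2)]/n}
- chance of a falsely significant difference = Φ[(p1 − p2 − 1.96 se0)/se1]

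For t = 5% and d = 0.25: p1 = 0.05, p2 = 0.0125, p̄ = 0.03125, se0 = 0.01100, se1 = 0.01094. This gives Φ[(0.0375 − 0.02157)/0.01094] = Φ(1.456) = 0.93. Expected counts are 25 against 6.25.

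For t = 1% and d = 0.75: p2 = 0.0075, p̄ = 0.00875, se0 and se1 both 0.00589. This gives Φ[(0.0025 − 0.01154)/0.00589] = Φ(−1.54) = 0.06. Expected counts are 5 against 3.75.

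| True rate t | d = 0.25 | d = 0.50 | d = 0.75 |
|---|---|---|---|
| 1% | 32% | 15% | 6% |
| 2% | 57% | 25% | 9% |
| 3% | 75% | 36% | 11% |
| 5% | 93% | 55% | 16% |

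A simulation of 200,000 trials per cell with the uncorrected chi-square test agrees within about 3 percentage points. With equal detection (d = 1) it rejects in 4.3% to 4.9% of trials.

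Testosterone concerns men only. Section 9.9 anticipates 931 men among 1,500 patients, or 931/1500 × 500 ≈ 310 per arm. At t = 5% the figures fall to 77%, 37% and 12%.

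**Step 5: analytes common to all arms.** These are not drawn equally often. Hematology and chemistry on HDI are at Days 1, 8, 15, 22 and 29, then every 4 weeks for 2 months and every 6 weeks after that. On ipilimumab they are at Days 1, 22, 43 and 64, then Week 12, then every 6 weeks in maintenance. As the extracted tables read (the HDI table may be broken), hormonal studies are marked at fewer visits on HDI.

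**The case against.** The strongest case against is that the reach is assumed. Section 9.7.1 only summarizes laboratory toxicities; the tests are in 9.8.2 and use data from the case report forms and CTEP-AERS. Whether an asymptomatic lipase or cortisol value is recorded as an AE depends on the Forms Packet, which is not among the documents. Section 9.8.2 does not say which terms make up its categories. The ipilimumab event list in 5.4 places raised lipase and amylase under Investigations, which is not one of the nine, and CPK belongs by name to none of them. This stands as a limit: the point applies to the individual terms and to whichever categories or totals contain them.

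A reader might also infer that the grade 3 or higher comparison is materially distorted. The documents do not show this. Their examples of low testosterone and adrenal insufficiency are grade 2. At 10 mg/kg, grade 3–4 endocrinopathy of all kinds was 2.4% (1.5.4.3), against 32.6% with drug-related grade 3/4/5 events in the phase II summary (1.5.4.6.1). The effect on the total may be small.

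A further objection is that symptomatic events are not lost: both calendars allow clinically indicated hormonal tests and collect AEs to 70 days after the last dose. That is right, and it confines the problem to laboratory-detected events. Nor is safety called the main secondary objective; 2.2.1 concerns ipilimumab at either dose and is not worded as a comparison with HDI. Section 9.8.2 nevertheless plans that comparison, and nothing in the plan guards it.

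**Conclusion.** The point holds within limits. Followed as written, 9.8.2 would compare ipilimumab with HDI on events that the schedule looks for in one arm and not the other. The affected results are laboratory-detected pancreatic, adrenal, testosterone and CPK abnormalities, and any category or total that includes them. The two ipilimumab doses share one calendar, so their comparison is sound on this point. RFS, OS, type I error allocation and sample size are unaffected.

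The size cannot be settled from the documents. The 6% to 93% range rests on assumed true rates, detection fractions and a two-sided 0.05 test. The low end is close to the nominal 5%. A reader might take the high end as the expected result, but no document supports either a 5% laboratory-only rate or 25% detection. The 7.6% any-grade endocrinopathy rate at 10 mg/kg includes clinical events, and pancreatitis, reported in under 1%, is not the same as an isolated enzyme rise.

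It would also be tempting to conclude that restricting tests to analytes common to all arms makes the comparison fair. The differing visit schedules do not support that. The change is worth making because the direction of bias is known and the cost is low.

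**What to change.** In 9.8.2:

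1. Identify laboratory-only events from amylase, lipase, ACTH, cortisol, testosterone and CPK, and do not formally test them between ipilimumab and HDI. Report them within arm, or between the 10 and 3 mg/kg arms.
2. State which AE terms form each category, so that it is clear where these events fall.
3. Present each affected category, and the grade 3 or higher comparison, with and without these events.
4. State that analytes scheduled in every arm are drawn at different visit frequencies, and attach that caveat to their ipilimumab-versus-HDI comparisons.

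The cost is SAP wording and a few extra tables. No new tests are needed.
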